**Virtual Reality Training System on Oral Health
Care for Dependency Elderly in Oral Hygiene
Students: A Randomized Controlled Trial**

NCT number: KMUHIRB-SV(II)-20200071

Date: 2020/10/27

Study protocol

Background

VR explores the revolution in medical training during COVID-19, when face-to-face training is not possible during a nationwide lockdown. VR can ease the burden and train medical professionals much more effectively than the traditional training methodologies[1]. Virtual reality (VR) has been proposed as a promising technology for higher education since the combination of immersive and interactive features enables experiential learning. Medical and healthcare students have limited opportunities to practice such skills in their clinical placements due to a lack of supervision and relevant practicing situations[2]. At present, VR is regarded as a training tool that can effectively train and implement and has been widely used in professional medical operations[3]. A previous study found that a VR training system provided students with better learning outcomes and self-confidence[4]. VR may also help improved knowledge retention, increase motivation to study, and decrease the fear of learning new things[2].

According to United Nations statistics [5], it is estimated that 15% of the population worldwide or some 1 billion individuals live with one or more disabling conditions. More than 46 per cent of older persons – those aged 60 years and over— have disabilities and more than 250 million older people experience moderate to severe disability. Taiwan has reached an age society in 2018 and the elderly population accounts for 14.1% of the total population and is expected to enter a super-aged society in 2025[6]. Poor oral health gives rise to considerable problems that impact both on an individual's well-being and quality of life as well as increasing the risks of general health issues[7]. Studies have pointed out that providing professional oral care can help reduce the risk of respiratory infections in elderly[8, 9]. An intervention study from Japan suggested that providing professional oral health care (POHC) by dental hygienists reducing prevalence of fever and is effective in preventing respiratory infections in elderly persons requiring nursing care[10]. The oral hygiene students expect to become professionals who can provide oral care for the elderly in the future. In their development education, it is imperative to strengthen their oral care skills for the elderly. With the strengthening of their skills, they will increase their self-efficacy. Possess professional oral care for the elderly to facilitate the implementation of oral care for the elderly in clinical work in the future. Oral hygiene students should not only have the correct oral health care knowledge and skills but should further learn to be effective in the subsequent clinical practice or work in the correct choice of oral care instruments, demonstrating and teaching patients or caregivers how to perform oral

health care properly, and then promote patient health care outcomes [11]. In addition to knowledge, there are also a series of operation steps and related equipment selection for the education and guidance of oral care. Therefore, it may be more difficult for students to have opportunities for self-operation and practice by simply teaching or demonstrating in class. Traditional physical teaching aids are also more challenging to simulate situations and even more challenging to have coherent step-by-step learning to overcome the difficulty of traditional teaching methods to achieve situational simulation and a series of practical exercises.

VR, in particular, has been adopted across medical and nursing fields as a method to educate medical students on some professional topics that require operational learning, such as emergency first aid, basic life-saving techniques, surgical skills training, learning systematic clinical observation and fire safety; the results show that the effectiveness is no less than that of using traditional teaching aids, especially the effectiveness of operating skills [12-14]. No study has developed and evaluated the effects of implement VR applications to train oral care professionals. We therefore developed the first VR system used in professional oral care training, which allows users to self-practice the elderly oral care skill in an immersive and interactive cave VR system (Pvix VR, EPED Inc.). The dependency elderly seniors are selected as the training objects in this VR training system because they were high risks groups, and the elderly's safety cannot be guaranteed if the students have not undergone sufficient practice and training. Therefore, we aimed to evaluate the effectiveness of VR-based training on oral health care for the dependency elderly among oral hygiene students.

Methods

2.1. Design and Participants

A randomized controlled trial (RCT) was conducted. The protocol was approved by the Institutional Review Board of Kaohsiung Medical University Hospital (reference numbers: KMUHIRB-SV(II)-20200071). All students provided informed consent before the participation.

A total of 23 students from the third grade of Department of Oral Hygiene students in Kaohsiung Medical University during the 2021 academic semester were recruited in the present study. Participants have to take both the courses of 'Basic Medical Nursing Care' and 'Oral Health Care for Community People and Long-term Care Residents' before intervention. Eleven students were randomized in the virtual-reality experimental group (EG) and 12 in the control group (CG).

2.2. Randomization and Allocation

Students were randomly assigned to the virtual-reality experimental (EG) group and control group (CG). We used the random table from Excel with a ratio of 1:1 to accomplish the randomization. An open-label experimental design was used; students

were wise to the group they were allocated in.

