2.6. Data Collection

The students in both groups self-completed a baseline questionnaire after the allocation. The post-test was collected immediately after each intervention, and the satisfaction survey was collected at the end of the whole intervention in the experimental group. As for the control group, the post-test was collected at 2-week (Time 2), 4-week (Time 3), and 6-week (Time 4) follow-ups.

Statistical Analysis Plan

This study explored the variables' relationships using STATA version 13.1 (Stata Corp LP, College Station, Texas, USA). Percentage, Fisher's exact test, and Wilcoxon rank-sum test were used to compare the VRG and CG demographic variables. Wilcoxon rank-sum test compares the difference of oral care-related knowledge, Attitude, self-efficacy, and intention within groups. Linear regression in generalized estimating equations (GEE) compares the difference of oral care-related knowledge, attitude, self-efficacy, and intention between groups. The effect size (Cohen's d) of continuous variables were calculated from the mean difference between baseline and the follow-ups between the VRG and CG. An effect of 0.20 is small, 0.50 is medium, and 0.80 is large[16].

[figure not shown]

Figure 1. CONSORT flow diagram

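### With 11 v 12 students a medium-sized chance baseline gap on at least one of four outcomes is about as likely as not or more so, and the analysis states no baseline adjustment to absorb it

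*Combined protocol and SAP*

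**What the plan says.** Section 2.1 gives the sample as "A total of 23 students from the third grade of Department of Oral Hygiene students in Kaohsiung Medical University", divided 11 to the VR arm and 12 to control. Section 2.2 gives the method: "We used the random table from Excel with a ratio of 1:1 to accomplish the randomization". It mentions no stratification, blocking or minimisation, and the design is open-label.

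Section 2.6 fixes when baseline is measured: "The students in both groups self-completed a baseline questionnaire after the allocation". Section 2.4.5 lists age and gender as the only covariates.

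Under the Statistical Analysis Plan heading, linear GEE "compares the difference of oral care-related knowledge, attitude, self-efficacy, and intention between groups". The sentence does not say whether baseline is an outcome row, a covariate or left out. Cohen's d values "were calculated from the mean difference between baseline and the follow-ups between the VRG and CG", and are labelled small, medium and large at 0.20, 0.50 and 0.80. No primary outcome is named.

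**The concern.** With arms this small, one random split can easily leave the groups visibly apart on the scores that will later be compared, and nothing in the described allocation limits that.

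The analysis would then have to deal with the gap, and as written it does not clearly do so. Subtracting baseline over-corrects whenever baseline and follow-up correlate below 1: the arm that starts higher by chance tends to gain less. Comparing follow-up scores alone under-corrects. In both cases part of the accident of the draw is reported as effect. The plan attaches a label to an effect as small as 0.20, so a carried-over gap of that order matters for interpretation.

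**Working it through.** The plan states no sample-size, power or imbalance figure, so there is nothing of its own to reproduce.

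**Inputs.** From the document: arms of 11 and 12 (section 2.1); four outcomes and the 0.20/0.50/0.80 labels (Statistical Analysis Plan). Assumed, because the document gives neither: correlation between outcomes of 0 to 0.7, and baseline-to-follow-up correlation r of 0.3 to 0.7. Scores are taken as normal with equal variance at both times, in SD units.

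**1. Size of the chance gap.** SD of the standardised baseline difference = √(1/11 + 1/12) = 0.417.

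- P(gap ≥ 0.5) = 2[1 − Φ(0.5/0.417)] = 23.1% per outcome.
- P(gap ≥ 0.8) = 2[1 − Φ(0.8/0.417)] = 5.5% per outcome.

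**2. At least one of four outcomes.** If independent, 1 − (1 − 0.231)⁴ = 65% for 0.5 SD and 1 − (1 − 0.055)⁴ = 20% for 0.8 SD. By simulation (60,000 draws per row, fixed 11/12 split):

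| Correlation between outcomes | Any gap ≥ 0.5 SD | Any gap ≥ 0.8 SD |
|---|---|---|
| 0 | 65% | 20% |
| 0.3 | 62% | 19% |
| 0.5 | 57% | 17% |
| 0.7 | 49% | 14% |

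If the gap is scaled by the sample SD (t, 21 df) under independence, the figures are 67% and 25%. Simple coin-flip allocation gives 67% to 51% for 0.5 SD over the same correlations, so the result hardly depends on which kind of Excel draw was used.

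**3. How much reaches the reported effect.** Given a baseline gap g, the change-score difference shifts on average by −(1 − r)g. P(shift ≥ 0.20) = 2[1 − Φ(0.20/((1 − r) × 0.417))].

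| r | Shift from a 0.5 SD gap | P(shift ≥ 0.20) |
|---|---|---|
| 0.3 | 0.35 | 49% |
| 0.5 | 0.25 | 34% |
| 0.7 | 0.15 | 11% |

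If the GEE used follow-up scores alone, the shift would be +r·g, which is 0.15, 0.25 and 0.35 in the same rows.

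**4. What a baseline covariate gains.** For a single follow-up:

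- Change score: SD = 0.417 × √[2(1 − r)].
- Baseline-adjusted: SD = 0.417 × √[(1 − r²)(1 + 1/19)]. The 1/19 is the price of estimating the slope with 21 within-group df (21 − 2 = 19).

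| r | Change score | Adjusted | Reduction |
|---|---|---|---|
| 0.3 | 0.494 | 0.409 | 17% |
| 0.5 | 0.417 | 0.371 | 11% |
| 0.7 | 0.323 | 0.306 | 5% |

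Simulation agrees with both columns to within 0.002.

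**5. What stratifying would add.** With a median split on one baseline score (6:6 and 5:6), the SD of the gap on that score falls from 0.417 to about 0.26, and P(gap ≥ 0.5) from 23% to 6%. The chance of such a gap on any of the four outcomes falls much less: from 65% to 57% at correlation 0, and from 57% to 47% at 0.5. Once the baseline term is in the model, the adjusted SD on the stratified outcome moves only from 0.409/0.371/0.306 to 0.401/0.365/0.300, about 2%.

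**The case against.** The strongest reply is that 1:1 randomisation is valid without stratification, chance imbalance is already reflected in the standard error, and allocation is over. All of that stands. The averages of repeated draws are unbiased, and the point is confined to precision and to how one realised draw is read.

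A second reply is that the change score already uses baseline. It does, but only partly: step 3 shows what is left, and step 4 shows that the covariate does better over the range of r considered. How much better depends on an r that the document does not give; near 0.7 the gain is modest.

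A reader might also infer three stronger claims that the document does not support:

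- *That a large gap is likely.* On the plan's scale large means 0.8 SD. The chance of that on at least one outcome is about 14% to 25%.
- *That the draw was unrestricted, with the full list fixed beforehand.* Neither is stated. A 1:1 ratio ending at 11 and 12 fits a forced equal split, and simple randomisation would also give an 11/12 split 32% of the time.
- *That a stratified draw would have cost nothing and solved the problem.* Section 2.6 places the baseline questionnaire after allocation, so no baseline score existed to stratify on. Results from the two required courses are not mentioned as available. Stratifying on one score would also leave three outcomes largely unprotected, with no primary outcome to guide the choice.

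**Conclusion.** The point holds as a low-severity improvement to the analysis; it does not show a fault in the randomisation. A baseline gap of at least 0.5 SD has a 23% chance per outcome and about 49% to 65% on at least one of four, for assumed correlations between outcomes of 0.7 to 0. With no stated baseline adjustment, a gap of that size shifts a change-score effect by about 0.15 to 0.35 SD for r from 0.7 to 0.3. At r of 0.6 or below, the shift is at least the plan's small threshold (0.5 × 0.4 = 0.20). Adjustment for baseline removes most of this and lowers the SD of the estimate by about 5% to 17%.

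The results rest on approximate normality, equal variances and the assumed correlations. They do not depend on whether the Excel draw was a coin-flip or a forced split.

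**What to change.** In the Statistical Analysis Plan, replace the between-group GEE sentence with text such as: *For each outcome, a linear GEE is fitted to the scores at Times 2, 3 and 4 with group, time, group by time and that outcome's own baseline score as covariates. The group effect is the baseline-adjusted difference. The standardised effect is that difference divided by the pooled baseline SD.* Whether the current model already includes baseline should be stated. If the present change-based d is retained, report it as secondary.

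The cost is one model term per outcome and no new data. One caution should be reported: baseline was self-completed after allocation in an open-label trial, so the covariate could itself reflect knowledge of the arm. The change score has the same weakness.

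For a new draw only, section 2.6 would have to place the baseline questionnaire before allocation. Section 2.2 could then stratify by a median split of one named baseline score and state the procedure in full. This lowers the chance of a 0.5 SD gap from 23% to 6% on that score but adds at most about 2% precision once the baseline term is in the model, so it is optional.

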2.3. Instrument

A structured questionnaire related to elderly oral health was developed to collect data on five parts: (1) demographics (i.e., gender, age), (2) oral care-related knowledge, (3) attitude toward oral care, (4) self-efficacy toward oral care (5) intention to oral care behaviors. A panel of experts reviewed items to assess content validity. The content validity index was 0.97-1.00. The reliability of each scale was assessed in terms of internal consistency (Cronbach's alpha coefficient). The satisfaction survey was based on System Usability Scale (SUS) to measure the usability of the VR-based learning system the students used during the oral care training. The SUS covered the effectiveness (the ability of users to complete tasks using the system, and the quality of the output of those tasks), efficiency (the level of resource consumed in performing tasks), and satisfaction (users' subjective reactions to using the system) [15].

2.4. Outcome Measures

2.4.1. Elderly oral care-related knowledge

Twenty items measured elderly oral care-related knowledge; for example, 'There is no need to consider the size of the interdental brush.' Possible responses included True (1), False (0), and I do not know (0), with possible scores ranged from 0 to 20; a higher score indicated a higher degree of oral-care-related knowledge. The KR-20 coefficient was 0.56 for this scale.

2.4.2. Attitude toward elderly oral care

Seven items measured attitude toward elderly oral care, for example, 'Assist disabled elderly to clean their teeth is annoying.' Each item was scored on a five-point Likert-type scale ranging from 1 (strongly disagree) to 5 (strongly agree). Possible scores ranged from 5 to 35; a higher score indicated a more positive attitude toward oral care for the elderly. Cronbach's alpha was 0.70 for this scale.

2.4.3 Self-efficacy of elderly oral care

Eleven items were used to evaluate the self-efficacy of elderly oral care. Students indicated their degrees of agreement with statements related to perceptions of personal ability concerning oral care for the elderly. For example, 'I am confident to remind disabled elderly having regular dental visits every six months.' Each item was scored on a five-point Likert-type scale ranging from 1 (strongly disagree) to 5 (strongly agree). Possible scores ranged from 5 to 55; a higher score indicated more substantial confidence toward oral care for the elderly. Cronbach's alpha was 0.87 for this scale.

2.4.4 Intention to elderly oral care behaviors

Twelve items were used to evaluate the intention to elderly oral care behavior for elderly. Students indicated their goals of adding new behaviors or modifying existing behaviors of oral care for the elderly. For example, 'I will take the initiative to assist disabled elderly to clean their dentures.' Each item was scored on a five-point Likert-type scale ranging from 1 (strongly disagree) to 5 (strongly agree).

2.4.5 Covariates

Age and gender were assessed at baseline for each student in this study.

2.5. Interventions

The VR-based training system (Pvix VR, EPED Inc.) equipped an optical portable wearable device that utilizes positioning motion recognition technology and a built-in virtual interactive software to assist in the self-training of future oral care personnel and health caregivers. Students are immersed in a 3D environment as soon as they put on the optical 3D glasses. The oral health interactive software stimulates diverse ability levels through the simulation of different actions. Students learn standard procedures of oral care through automatic assessment. In addition, the software customizes standard process courses and teaching plans in several fields.

The students in EG received VR-based training for elderly oral health care at 2-week (Time 2), 4-week (Time 3), and 6-week (Time 4) follow-ups. The learning module was divided into three sessions according to the physical condition (1) Mild disability, (2) Semi-disability, (3) Total disability and oral condition, (1) wearing dentures, (2) missing teeth of the elderly (Figure 2.). Students simulate the different physical and oral conditions of the elderly through virtual situations and provide suitable oral care methods. The whole training session took approximately two hours for each student; First, students were first given a short introduction to the VR system's use (10 minutes). Second, they were able to carry out oral care for the elderly while wearing VR goggles and using hand-controllers with the teaching and audio guides during the process (90 minutes), and an evaluation was taken after the intervention (20 minutes).

The students in CG do not receive any of the interventions. However, the same VR-based curriculum of oral health care on dependency elderly were provided at the end of the study.

2.6. Data Collection

The students in both groups self-completed a baseline questionnaire after the allocation. The post-test was collected immediately after each intervention, and the satisfaction survey was collected at the end of the whole intervention in the experimental group. As for the control group, the post-test was collected at 2-week (Time 2), 4-week (Time 3), and 6-week (Time 4) follow-ups.

Statistical Analysis Plan

This study explored the variables' relationships using STATA version 13.1 (Stata Corp LP, College Station, Texas, USA). Percentage, Fisher's exact test, and Wilcoxon rank-sum test were used to compare the VRG and CG demographic variables. Wilcoxon rank-sum test compares the difference of oral care-related knowledge, Attitude, self-efficacy, and intention within groups. Linear regression in generalized estimating equations (GEE) compares the difference of oral care-related knowledge, attitude, self-efficacy, and intention between groups. The effect size (Cohen's d) of continuous variables were calculated from the mean difference between baseline and the follow-ups between the VRG and CG. An effect of 0.20 is small, 0.50 is medium, and 0.80 is large[16].

[figure not shown]

Figure 1. CONSORT flow diagram

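### The baseline questionnaire is self-completed after allocation in an open-label trial, so the change-from-baseline effect size can be biased by an amount and in a direction that cannot be determined

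*Combined protocol and SAP*

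**What the plan says.** Section 2.6 (Data Collection) sets the order of events: "The students in both groups self-completed a baseline questionnaire after the allocation". Section 2.2 calls the trial open-label and says that students "were wise to the group they were allocated in". It does not say when they were told.

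Attitude, self-efficacy and intention (sections 2.4.2 to 2.4.4) are self-rated. For attitude, "Each item was scored on a five-point Likert-type scale", and the other two scales use the same format. Self-efficacy asks for agreement with "statements related to perceptions of personal ability concerning oral care for the elderly". Knowledge (section 2.4.1) is a 20-item test marked right or wrong.

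The Statistical Analysis Plan says that Cohen's d is "calculated from the mean difference between baseline and the follow-ups between the VRG and CG". For the between-group comparison, "Linear regression in generalized estimating equations (GEE) compares the difference of oral care-related knowledge, attitude, self-efficacy, and intention between groups". It does not say whether the baseline score is an outcome time point, a covariate or unused in that model. The section on covariates (2.4.5) names two variables only: "Age and gender were assessed at baseline for each student in this study".

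**The concern.** A baseline measurement should be free of any influence of allocation. Here it is taken after allocation, in students who probably already knew their arm. A student who knows that VR training is coming, or that no training will be given until the study ends, may answer items on confidence, attitude or intention differently. The right-or-wrong knowledge test is less exposed.

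Cohen's d subtracts this baseline. A reporting shift that differs between arms at baseline and has partly or wholly gone by follow-up is therefore carried into the effect size as if it were a training effect, or as the loss of one. Whether the GEE result carries the same bias depends on how baseline enters the model, which is not stated.

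A between-arm baseline difference also loses its usual meaning. It could be chance or a reporting shift, and the data cannot separate the two.

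**Working it through.** The plan gives no SD, expected effect or power figure, so there is no number of its own to reproduce. The check is algebraic, with a simulation to confirm it.

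**Inputs from the documents.** Arms of 11 and 12 (section 2.1); baseline after allocation (2.6); open label (2.2); d based on change from baseline, with benchmarks 0.20, 0.50 and 0.80 (Statistical Analysis Plan).

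**Assumed quantities.** b is the baseline reporting shift, experimental minus control. k is the share of it still present at follow-up. rho is the correlation between baseline and follow-up score. The documents give none of these.

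**Bias by type of contrast, with equal SDs:**

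- Change score, or GEE with baseline as an outcome time point and a group-by-time term: kb - b = (k-1)b
- GEE with baseline as a covariate: about kb - rho·b = (k-rho)b
- GEE on the post-tests only: kb

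| Contrast | k = 0 | k = 0.5 | k = 1 |
|---|---|---|---|
| Change score, or group-by-time GEE | -b | -0.5b | 0 |
| Baseline as covariate, rho = 0.3 | -0.3b | +0.2b | +0.7b |
| Baseline as covariate, rho = 0.7 | -0.7b | -0.2b | +0.3b |
| Post-tests only | 0 | +0.5b | +b |

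If the shift is the same in both arms, b = 0 and every entry is 0. A simulation with 20,000 students, four time points, an exchangeable GEE and b = 1 agreed with every entry to within 0.03.

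**At the trial's own size.** Simulated trials with arms of 11 and 12, assuming a true difference of 0.50 SD and rho = 0.5, gave these mean estimates:

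| Assumed b (SD) | k | Change score | Baseline as covariate | Post only |
|---|---|---|---|---|
| 0 | – | 0.50 | 0.50 | 0.50 |
| -0.5 | 0 | 1.01 | 0.75 | 0.50 |
| -0.2 | 0 | 0.70 | 0.61 | 0.51 |
| +0.2 | 0 | 0.30 | 0.40 | 0.49 |
| +0.5 | 0 | -0.01 | 0.24 | 0.49 |
| +0.5 | 1 | 0.50 | 0.75 | 1.00 |

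A shift of 0.5 SD common to both arms left all three at 0.50.

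**Choice of SD.** The plan does not say which SD standardises d. If it is the SD of the change, the bias for k = 0 is -b/sqrt(2(1-rho)). At b = 0.5 this is 0.5/sqrt(1.4) = 0.42 in size for rho = 0.3, and 0.5/sqrt(0.6) = 0.65 for rho = 0.7.

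**Could such a shift be seen?** The standard error of a chance baseline difference is sqrt(1/11 + 1/12) = 0.417 SD. A shift of 0.5 SD is 0.5/0.417 = 1.2 standard errors and one of 0.2 SD is about 0.5, so neither could be told from chance. The plan's between-arm comparison at baseline covers demographic variables only, not the outcome scores.

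**After moving baseline before randomisation.** The baseline component is 0. The change-score, covariate and post-only contrasts then all carry the same remaining open-label bias at follow-up, kb.

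**The case against.** The strongest case is that this is a risk, not a demonstrated error. Three conditions must hold: students knew their group when they answered, the shift differed between arms, and it did not fully persist. None is shown. The flow diagram, which might show the sequence, is not reproduced in the available text and cannot count against the plan. This stands: awareness at baseline is a strong inference only, and the size and direction of any bias are unknown.

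Second, moving the baseline need not reduce net bias. The change-score bias goes from (k-1)b to kb, which is smaller only when k is below 0.5. At k = 1 it goes from 0 to b. Students know their group throughout, so a persisting shift is plausible. This also stands. The case for the change is that allocation can no longer influence the baseline, so any imbalance in it can be read as chance. It does not rest on a guaranteed smaller bias.

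Third, reading imbalance as chance needs more than earlier timing, because section 2.2 describes no allocation concealment. That is met by opening the allocation list only after all baselines are returned.

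Fourth, the follow-ups are labelled Time 2 to Time 4, which hints that baseline is Time 1 in the GEE. It is only a hint. If it is right, a group-by-time contrast carries the same (k-1)b as the change score. How baseline enters the model is a specification gap in its own right and adds no weight here.

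Finally, the past tense in sections 2.1 and 2.6 suggests that baselines are already collected, in which case only disclosure is possible.

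**Conclusion.** The concern holds. Section 2.6 places a self-reported baseline after allocation in an open-label trial, and the planned effect size depends directly on it. The change-score bias is (k-1)b. It vanishes only if the shift is equal in both arms or persists fully.

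No actual figure can be given, because b and k are not in the documents. On the assumption that none of the shift persists and that d is standardised by the baseline SD, a shift of 0.2 to 0.5 SD moves d by the same amount in the opposite direction. That is enough to change its label as small, medium or large. The conclusion rests on students having known their arm at baseline, which is likely but not stated, and it applies mainly to attitude, self-efficacy and intention.

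The timing should be changed if it still can be. If not, the result needs a plain caveat, since no analysis can remove the bias afterwards.

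**What to change.** **If baseline is not yet collected,** change section 2.6 to read: *All students complete the baseline questionnaire before randomisation; the allocation list is opened only after all baseline questionnaires are returned.* The only cost is giving the same questionnaire earlier. This removes the baseline component, not open-label reporting bias at follow-up.

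**If baseline is already collected:**

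1. State in section 2.6 when students learned their group relative to completing the baseline questionnaire.
2. Report baseline knowledge, attitude, self-efficacy and intention scores by arm.
3. State the possible bias as a limitation, and say how baseline enters the GEE.

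This takes a timing sentence, one table, a limitation sentence and a line on the model, with no new data.

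Optionally, show the raw Time 4 between-group difference beside the change-score result. It carries bias kb where the change score carries (k-1)b, so it cannot settle which is right. Nor does it correct chance baseline imbalance, whose standard error is about 0.42 SD with these arms.

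### The SAP names an independent-samples test, the Wilcoxon rank-sum, for within-group comparisons of paired scores

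*Combined protocol and SAP*

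**What the plan says.** The Statistical Analysis Plan assigns three comparisons in consecutive sentences.

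- Demographics between groups: percentages, Fisher's exact test and "Wilcoxon rank-sum test were used to compare the VRG and CG demographic variables".
- Outcomes within groups: "Wilcoxon rank-sum test compares the difference of oral care-related knowledge, Attitude, self-efficacy, and intention within groups".
- Outcomes between groups: "Linear regression in generalized estimating equations (GEE) compares the difference of oral care-related knowledge, attitude, self-efficacy, and intention between groups".

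Section 2.6 shows that each student is measured repeatedly. At baseline, "The students in both groups self-completed a baseline questionnaire after the allocation". In the VR group, "The post-test was collected immediately after each intervention", and section 2.5 places the three sessions at weeks 2, 4 and 6. In the control group, "the post-test was collected at 2-week (Time 2), 4-week (Time 3), and 6-week (Time 4) follow-ups". Section 2.1 gives 11 students in the VR group and 12 in the control group. Neither the signed-rank test nor any other paired test is mentioned.

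**The concern.** A within-group comparison of baseline with follow-up uses two scores from each student. The rank-sum test ignores that link and treats 11 pairs as 22 unrelated people. The preceding sentence names the same test for VR against control, where the samples really are independent, so the plan applies one test to two different data structures.

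If a student's scores are positively correlated over time, the variance assumed by the rank-sum test is too large for the comparison. Its p-values then tend to be too large, and a true change from baseline may be reported as no change. False positives are not inflated in that case.

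**Working it through.** The plan gives no alpha, power, sample-size calculation or within-student correlation, so there is no figure of its own to reproduce. The check is a simulation under stated assumptions.

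**Inputs from the documents**
- Pairs per within-group test: 11 (VR) and 12 (control), section 2.1.
- Gains of 0.5 and 0.8 SD, borrowed from the plan's own benchmarks: "An effect of 0.20 is small, 0.50 is medium, and 0.80 is large". The plan gives these for a between-group Cohen's d; here they serve only as illustrative within-group shifts.

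**Assumptions not in the documents**
- Two-sided alpha 0.05, bivariate normal scores with equal SD, and correlation ρ between a student's two scores.

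**Why the direction is as stated.** With SD σ and n pairs, the variance of the mean change is 2σ²(1−ρ)/n. Treating the samples as independent uses 2σ²/n. The assumed standard error is therefore too large by a factor 1/√(1−ρ): 1/√0.7 = 1.20, 1/√0.5 = 1.41 and 1/√0.3 = 1.83 for ρ = 0.3, 0.5 and 0.7. The rank tests follow the same logic approximately.

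**Simulation.** There were 20,000 data sets per setting, with both tests by normal approximation without continuity correction. The Monte Carlo standard error is at most √(0.25/20,000) = 0.35 percentage points. Each cell gives the rejection rate for rank-sum / signed-rank.

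| n | Gain | ρ = 0 | ρ = 0.3 | ρ = 0.5 | ρ = 0.7 |
|---|---|---|---|---|---|
| 11 | 0 | 4.9% / 4.0% | 2.3% / 4.1% | 0.8% / 4.2% | 0.2% / 4.1% |
| 11 | 0.5 SD | 18% / 16% | 15% / 22% | 12% / 28% | 9% / 45% |
| 11 | 0.8 SD | 40% / 35% | 39% / 48% | 38% / 62% | 38% / 84% |
| 12 | 0 | 4.9% / 4.9% | 2.3% / 5.1% | 1.2% / 5.2% | 0.3% / 5.7% |
| 12 | 0.8 SD | 45% / 43% | 45% / 57% | 44% / 70% | 45% / 89% |

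At n = 12 the choice between normal approximation and exact critical values matters slightly. The signed-rank statistic has mean 12·13/4 = 39 and variance 12·13·25/24 = 162.5, so the approximation rejects at 39 − 1.96·√162.5 = 14.0, that is, at 14 or below. The exact cut-off is 13. With both tests exact, power for 0.8 SD at ρ = 0.3 / 0.5 / 0.7 is 42% / 41% / 42% for rank-sum and 52% / 67% / 87% for signed-rank. The gap remains.

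**Effect on p-values.** At n = 11, ρ = 0.5 and a 0.8 SD gain, the median p-value is 0.082 by rank-sum and 0.026 by signed-rank. At n = 11 and 0.5 SD, the rank-sum p-value is the larger one in 65% / 79% / 92% of data sets for ρ = 0.3 / 0.5 / 0.7.

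**Where the pattern stops**
- At ρ = 0 nothing is lost.
- At ρ = −0.3 the direction reverses: rank-sum rejects 7.6% (n = 11) and 8.6% (n = 12) of the time when there is no change.
- In a single data set rank-sum can give the smaller p-value. With complete separation at n = 11, exact rank-sum gives 2/C(22,11) = 2/705,432 = 0.000003, and exact signed-rank gives 2/2¹¹ = 0.001.

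**Integer scores and ties.** For scores rounded to whole numbers (assumed mean 14, SD 3; 3,000 data sets per setting), n = 11, 0.8 SD and ρ = 0.5, power is 38.5% against 64.7%. For a 0–20 scale with a ceiling (assumed mean 17, SD 2), n = 11 and 0.8 SD, it is 38% / 38% / 37% against 47% / 60% / 79% at ρ = 0.3 / 0.5 / 0.7.

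**The case against.** The strongest reply is that this may be only a slip of the pen. If signed-rank was meant and run, no reported p-value changes. The documents cannot settle this. It limits the consequence but does not rescue the text, because an analyst following it would run the wrong test.

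A second reading is that rank-sum was to be applied to change scores, VR against control, which would be valid. The sentence says within groups, however, and the next one gives the between-group comparison to GEE. Under that reading the sentence would still need correcting.

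Third, the size of the loss rests on an assumed correlation and runs from modest at 0.3 to large at 0.7. That is fair. For the knowledge scale, a KR-20 of 0.56 (section 2.4.1) makes a pre–post correlation as high as 0.7 less likely, though it does not exclude it. The sentence also does not say which time points are compared.

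Fourth, within-group p-values do not answer the randomized question. This stands, and it is why the point is minor.

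**Conclusion.** The concern holds as a minor error in the named method. The wording is wrong for paired data, and no other part of the plan supplies a paired within-group test. Under positive within-student correlation the consequence is lost power, not extra false positives: at n = 11 and a 0.8 SD gain, about 9 percentage points at ρ = 0.3, 24 at 0.5 and 46 at 0.7. These sizes depend on the assumed alpha, normality and correlation, and on rank-sum actually being run. The tendency does not hold in every data set and would reverse under negative correlation. The GEE comparison and Cohen's d do not use this test, so the main judgement on VR training is not threatened.

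**What to change.** For within-group comparisons, replace the rank-sum test with the Wilcoxon signed-rank test on each student's follow-up minus baseline score, and state which time points are compared. Keep rank-sum for comparisons of the two independent groups.

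If the text is only a slip, the cost is one term. If rank-sum was actually run, the within-group p-values must be recomputed from existing data for 4 outcomes × 2 groups: 8 if only baseline to Time 4 is tested (×1), 24 if each follow-up is tested against baseline (×3), and 48 if all pairs of the four time points are tested (×6). No new data are needed.

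If within-group change is taken from GEE time contrasts instead, a small-sample correction is needed, for example t critical values with a bias-corrected variance. The plan does not state its variance estimator. If it is the robust one with normal critical values, a baseline-to-follow-up contrast on complete, normal pairs has a false-positive rate of 2·P(t with n−1 df > 1.96·√((n−1)/n)) = 9.1% at n = 11 and 8.7% at n = 12. With an n/(n−1) multiplier it is 2·P(t with n−1 df > 1.96) = 7.8% and 7.6%.
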